12.7.1. Primary Efficacy Analysis

The primary efficacy endpoint is the change from baseline to Month 12 in the total area of GA lesion(s) in eyes injected with pegcetacoplan, either monthly (PM) or every-other month (PEOM), or sham injections. GA lesion area (mm²) as measured by a quantified central reading center based on FAF images. The primary analysis will be the comparison of pegcetacoplan, either monthly (PM) or every-other month (PEOM) versus the combined 2 sham arms (the 2 sham arms will be combined into a single 'control' group).

The null and alternative hypotheses for the primary efficacy analysis are:

```
H_0: \mu_S = \mu_{PM} vs H_A: \mu_S \neq \mu_{PM}, and H_0: \mu_S = \mu_{PEOM} vs H_A: \mu_S \neq \mu_{PEOM}
```

Note: here μ indicates each group's respective mean change from baseline to Month 12 in GA lesion area for the comparison of the primary endpoint.

A mixed effect model for longitudinal data will be used to analyze the change from baseline in GA lesion area. The model will include treatment and presence of CNV in the fellow eye as fixed effects; baseline GA lesion area (at screening), time (in months) as a factor; as well as the time × treatment interaction term. All available data up to 12 months will be included in the model for the primary analysis. The mean change from baseline to 12 months will be estimated from the model (ie, least square [LS] mean) and compared between each of the pegcetacoplan arms to the sham control. For other time point of interest, LS mean change from baseline will be estimated and compared between treatments. Unstructured variance covariance will be used.

For the analysis of final study data, a similar model including data up to 24 months will be used and LS means at time points of interest will be estimated and compared between treatment.

As indicated in an earlier section, the study is expected to have an approximately 5 DMC data reviews. Allocating an alpha level of 0.0001 for each DMC data review, the alpha level remains for the efficacy analysis at 0.0495 to maintain an overall study alpha of 0.05.

The hypothesis testing strategy for the primary and secondary efficacy endpoints will be based on the Gate-keeping multiple testing procedures controlling for the study wide type I error strongly at 2-sided 0.0495 as follows:

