### For primary efficacy endpoint

- Presence of CNV in the fellow eye (yes; no)
- Baseline GA lesion area ( $< 7.5 \text{ mm}^2$  or  $\geq 7.5 \text{ mm}^2$ )

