### For key secondary, secondary, and exploratory endpoints

- Presence of CNV in the fellow eye (yes; no)
- Baseline GA lesion area ( $< 7.5 \text{ mm}^2$  or  $\geq 7.5 \text{ mm}^2$ )
- Baseline value of the endpoint

Of note, the randomization stratification factors were assessed at the screening visit. In the event of a change in status in the GA lesion area between the screening visit and the baseline visit (i.e., GA lesion area  $< 7.5 \text{ mm}^2$  at screening to  $\geq 7.5 \text{ mm}^2$ ) then the baseline status will be used.

If a statistical model is not directly specified and if necessary, data will be analyzed with the following approaches:

- For continuous endpoints, the MMRM analysis described for the primary endpoint in Section 6.2.2.
- For categorical or ordinal variables, a Cochran Mantel Haenszel (CMH) test with the baseline category status, presence of CNV in the fellow eye (yes or no), and baseline GA lesion area ( $< 7.5 \text{ mm}^2$  or  $\geq 7.5 \text{ mm}^2$ ) as stratification factors.

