### 6.2.2. Main Analysis of Primary Efficacy Endpoint

The primary endpoint will be analyzed in the mITT population with subjects grouped according to the treatment assigned at randomization.

A MMRM model will be used to analyze the primary endpoint. The analysis model will include treatment (PM, PEOM, sham), presence of choroidal neovascularization in the fellow eye at baseline (Yes, No) and baseline GA lesion area ( $< 7.5 \text{ mm}^2$  or  $\geq 7.5 \text{ mm}^2$ ) as fixed effects, time (study month, categorical) as a factor, the time  $\times$  treatment interaction term, and the baseline GA lesion area ( $< 7.5 \text{ mm}^2$  or  $\geq 7.5 \text{ mm}^2$ )  $\times$  time interaction term. The least square [LS] mean change from baseline to Month 12 will be estimated from the model for each of three arms as well as the comparisons of each of the three arms to each other. For other time points of interest, LS mean change from baseline will be estimated and compared between treatments. For each estimated LS mean, the corresponding 95% CI will be presented based on the model. For the comparison of the LS means, the corresponding 95% CI and the 2-sided P-value along with the percentage difference (difference in LS means between the arms/the comparison group LS mean) will be

presented. A common unstructured covariance matrix will be used to model the within-subject errors, the sandwich estimator (Diggle, Liang, and Zeger 1994) will be used to estimate the standard errors of the fixed effects parameters, and the degrees of freedom will be partitioned into between-subject and within-subject portions. If there are convergence problems with the model, then a heterogeneous autoregressive (1) covariance matrix will be used. If convergence problems still exist, an autoregressive (1) covariance matrix will be used. The LS mean of the change from baseline in the total area of GA lesion(s)  $\pm$  the standard error will be plotted over time by treatment group.

The observed values for the total area of GA lesion(s) will be summarized by treatment group and visit for both the study and the fellow eye. Summaries will present the descriptive statistics for baseline, absolute values and change from baseline data by visit.

The mean change from baseline in the total area of GA lesion (s) in the study eye  $\pm$  the standard error will be plotted over time by treatment group.

All GA lesion (s) size data will be listed for the ITT set.

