## 15. CHANGES TO ANALYSIS SPECIFIED IN PROTOCOL

The following changes were made to the analyses specified in the protocol

- The mITT set, which includes subjects with a baseline and at least one post-baseline GA lesion assessment, replaced the ITT set as the main efficacy population to be aligned with the primary analysis methodology.
- The change in GA lesion(s) size at Month 24 between PM and Sham was to be the third hypothesis tested in the hypotheses testing strategy as specified in the protocol. This was removed from the hypotheses testing strategy in the SAP.
- The change from baseline in mean threshold sensitivity in all points evaluating the macular functional response at Month 24 was promoted from secondary in the protocol to a key secondary efficacy endpoint here and included in the hypotheses testing algorithm.
- The hypotheses testing strategy and  $\alpha$  allocation for the key secondary endpoints was not precisely specified within the protocol and has been clarified to follow the hypotheses testing procedure and  $\alpha$  allocation as described in Section 6.3.1.
- Several new microperimetry endpoints were specified in the SAP that were not noted in the protocol.
  - Change from baseline in the mean threshold sensitivity within 500 microns outside the GA lesion, (perilesional points) assessed by mesopic microperimetry over time.
  - Change from baseline in 95% bivariate contour ellipse area (BCEA) over time.
  - Change from baseline in the mean threshold sensitivity of points beyond 500 microns outside the atrophy border (paralesional points) over time.
  - Change from baseline in the mean threshold sensitivity of points beyond the GA lesion (extralesional points) over time.
  - Number of points with clinically significant progression over time.
- Several new exploratory endpoints not specified in the protocol were added.
  - NEI-VFQ-39 distance activity, composite, near activity subscale score
  - NEI-VFQ-25 driving subscale score
  - Progression from iRORA to cRORA
  - Progression from large drusen to iRORA or cRORA
  - Change in the distance of the atrophy junction to the fovea and without subfoveal atrophy to subfoveal atrophy conversion
- No pre-specified analysis will be performed on the secondary endpoint of change from baseline in LLD over time. This data will only be listed.

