### 1.2.1. Mixed Effect Model for Repeated Measure

```
-----  
* Read Analysis data  
-----  
* In this example, repeated measures are available at  
* avisitn = 0.5 (baseline), 2 (Month 2),  
* 6 (Month 6), and 12 (Month 12)  
-----;
```

```
data ga;  
  set adam.adga;  
  if paramcd = 'SEGAORG' and  
    avisitn in (0.5, 2, 6, 12) and  
    ANL01FL = 'Y';  
  
  * trtan (actual treatment[number])  
  * 1 = APL-2 Monthly  
  * 2 = APL-2 Every Other Month  
  * 3 = pooled Sham group;  
  if trtan in (4,5) then trtan = 3;  
  
  * trt01 are trt02 are used in multiple imputation  
  * trt01 = 1 if Sham group  
  * trt02 = 1 if APL2 Monthly group  
  * trt01 = trt02 = 0 for APL2 EOM group;  
  if trtan = 3 then trt01= 1; else trt01 = 0;  
  if trtan = 1 then trt02= 1; else trt02 = 0;  
  
  * avisitc will be used in PROC TRANSPOSE;  
  if avisitn = 0.5 then avisitc = '00'; * Baseline;  
  if avisitn = 2 then avisitc = '02'; * Month 2;  
  if avisitn = 6 then avisitc = '06'; * Month 6;  
  if avisitn = 12 then avisitc= '12'; * Month 12;  
run;
```

```
*****;  
*** MAIN ANALYSIS using MMRM ***;  
*****;
```

```
proc mixed data=ga method=reml covtest empirical;  
  where avisitn NE 0.5; * exclude rows for baseline;  
  * cnv (CNV in the fellow eye)  
  * 0 = No  
  * 1 = Yes;  
  *base cat (baseline lesion size (<7.5 vs. ≥ 7.5));  
  class trtan cnv avisitn usubjid base_cat;  
  model chg = trtan cnv base_cat avisitn trtan*avisitn base_cat*avisitn  
  /cl;
```

```
repeated avisitn / subject=usubjid type=un r;  
lsmeans trtan*avisitn/pdiff cl e alpha=.05;  
ods output diffs= diff1 LSMeans= LSMean1;  
run;
```

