## 1.2.2. Multiple Imputation

```
*****;  
*** RESHAPE DATA FOR PROC MI ***;  
*****;  
  
proc sort data= ga;  
by usubjid cnv trta trtan trt01 trt02 param paramcd base base_cat avisitc;  
run;  
  
proc transpose data= ga out= ga_t(drop= _NAME_ _LABEL_) prefix=V;  
by usubjid cnv trta trtan trt01 trt02 param paramcd base base_cat;  
id avisitc;  
var aval;  
run;  
  
* Examine the missing patterns of the data;  
proc mi data=ga_t nimpute=0;  
var cnv trtan v00 -- v12;  
ods output missPattern=pattern;  
run;  
  
*****;  
*** MCMC (impute nonmonotone missing) ***;  
*****;  
  
* Below statements invoke MCMC procedure and specify IMPUTE=MONOTONE  
to turn the arbitrary missing patterns to monotone missing patterns  
under missing at random (MAR) assumption;  
  
proc mi data=ga t out=ga t mono seed= 12135541 nimpute=1000;  
mcmc chain=multiple impute= monotone displayinit  
initial=em(itprint);  
var cnv trt01 trt02 v00 -- v12;  
run;  
  
* Examine the missing patterns of the data;  
proc mi data=ga_t_mono nimpute=0;  
var cnv trt01 trt02 v00 -- v12;  
ods output missPattern=pattern;  
run;  
  
*****;  
*** Control-based pattern imputation(impute monotone missing) ***;  
*****;  
data ga t mono2;  
set ga t mono;  
**Identify the subjects in the active groups we want to keep  
imputed as MAR;  
**DSCREASN is just an example;  
if trtan in (1,2) and DCSREASN = 1 then mar = 1;  
else mar = 0;
```

```
run;

**First impute general MAR based on regression method for all subjects to get
the true MAR;
proc mi data=ga t_mono2 out=ga_step1 nimpute=1 seed=1284054;
  by Imputation_;
  class trtan;
  monotone reg(v00 -- v12/details);
  var cnv trtan v00 -- v12;
run;

**Identify and keep the data from the subjects in the active group that
should remain as a MAR;
data ga_step2;
  set ga_step1;
  if Mar = 1;
run;

**Update the dataset and keep the MAR imputed data for the subjects in the
active group that should remain as a MAR, all others remain to be imputed
with control based imputation;
data ga_t_mono3;
  update ga t_mono2 ga_step2;
  by Imputation_subjid;
run;

**Fill out the remaining missing where missing data should be imputed based
on the controls;
proc mi data=ga t_mono3 out=ga_t_cbp nimpute=1 seed=1284054;
  by imputation_;
  class trtan;
  var cnv v00 -- v12;
  monotone reg(/details);
  mmar model(v02 -- v12 / modelobs= (trtan='3'));
run;

**General control based (all monotone missing);
proc mi data=ga_t_mono out=ga_t_cbp2 nimpute=1 seed=1284054;

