  by imputation_;
  class trtan;
  var cnv v00 -- v12;
  monotone reg(/details);
  mmar model(v02 -- v12 / modelobs= (trtan='3'));
run;

*****;
*** Delta-Adjusted Pattern Imputation (impute monotone missing) ***;
*****;
**First identify the subjects in the active treatment groups that we want to
apply the shift parameter if they have monotone missing data;
data ga t_mono2;
  set ga_t_mono;

  **This is just an example of a reason that we do not want to
  apply the shift parameter. The actual reasons are in the text;
  if DCSREAS1 = "Death" then flag = 1;
  else flag = 0;
```

```
        if trtan in (1,2) and flag = 0 then adjustthis = 1;
        else adjustthis = 0;
    run;

proc mi data=ga t_mono2 out=ga_t_tip6 nimpute=1 seed=9484353;
  by _imputation_;
  class trtan adjustthis;
  var cnv trtan v00 -- v12;
  monotone reg(/details);
  mnar adjust(v02 / shift=0.12 adjustobs=(adjustthis = '1' ))
    adjust(v06 / shift=0.12 adjustobs=(adjustthis = '1' ))
    adjust(v12 / shift=0.12 adjustobs=(adjustthis = '1' ));
run;
*****;
*** SAS macro to run MIANALYZE on outputs from MMRM *;
*****;

%macro mi_results(in, lsm, dif);

* After imputation, the data sets are in the wide format in which
different variables (V00--V12) represent the outcome measured at
different occasions. Before analyzing using PROC MIXED,
the data sets need to be converted into long format in which one
variable represents all outcome with different values of AVISITN
differentiating different occasions;

proc transpose data= &in
  out= ga mi (rename= ( NAME = AVISITN COL1 = AVAL));
  by imputation usubjid trta trtan trt01 trt02 param paramcd base base_cat;
  var V00 -- V12;
run;

data ga_mi;
  set ga mi;
  label AVISITN = 'AVISITN';
  chg = aval - base;
  * baseline record is not used in MMRM;
  if AVISITN = 'V00' then delete;
run;

proc sort; by _imputation_; run;

proc mixed data=ga_mi method=reml empirical;
  by imputation ;
  class trtan cnv avisitn usubjid base_cat;
  model chg=trtan cnv base_cat avisitn trtan*avisitn base_cat*avisitn /cl;
  repeated avisitn / subject=usubjid type=UN;
  lsmeans trtan*avisitn / pdiff cl alpha=.05;
  ods output diffs= diffs lsmeans= lsmeans;
run;

* In the final step, the analysis results obtained from PROC MIXED
procedure are combined into a single estimation with standard error
using PROC MIANALYZE;

proc sort data=lsmeans;
```

```
by avisitn trtan _imputation_;
run;
proc mianalyze parms=lsmeans;
  by avisitn trtan;
  modeleffects trtan*avisitn;

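### The primary MMRM uses baseline GA area only as below versus at or above 7.5 mm²; adding the continuous value already held would gain some precision at almost no cost

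*SAP*

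**What the plan says.** SAP 6.2.2 lists the fixed effects of the primary MMRM as treatment, "presence of choroidal neovascularization in the fellow eye at baseline (Yes, No) and baseline GA lesion area" in two levels (below 7.5 mm²; 7.5 mm² or more), visit, and the interactions of visit with treatment and with that two-level factor. The covariate list in SAP 6 headed "For primary efficacy endpoint" gives the same two baseline terms. The sample code agrees: "model chg = trtan cnv base_cat avisitn trtan*avisitn base_cat*avisitn" in Appendix 1.2.1, and "model chg=trtan cnv base_cat avisitn trtan*avisitn base_cat*avisitn" in the analysis step after multiple imputation in Appendix 1.2.2. There `base_cat` is the two-level factor.

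The continuous value is at hand. The data-reshaping step in Appendix 1.2.2 carries both versions: "by usubjid cnv trta trtan trt01 trt02 param paramcd base base_cat avisitc". The imputation models use the continuous baseline, but the analysis that follows returns to the category.

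For key secondary, secondary and exploratory endpoints, SAP 6 adds a third covariate, "Baseline value of the endpoint". SAP 6.3.2 implements it for each key secondary endpoint, with a visit interaction. Protocol 12.7.1 describes the primary model as having "presence of CNV in the fellow eye as fixed effects; baseline GA lesion area (at screening), time (in months) as a factor".

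**The concern.** Protocol 6.1.1 admits lesions from 2.5 to 17.5 mm², so the upper category alone is 10 mm² wide and lesions of 7.6 and 17.4 mm² are treated alike. If larger lesions grow faster within a category, that variation, and any chance imbalance in it between arms, stays in the error term. Standard errors are then larger than they need be.

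The comparison with something to gain is PEOM versus sham, with stated power of 81.5% at SD 1.50. Both routes to the key secondary tests in SAP 6.3.1 require it to be significant: the pooled route needs both primary tests in both studies, and the fallback route needs both in this one. The two lesion-size subgroups are also affected. SAP 6.2.5 drops covariates made irrelevant by the subgroup, so no adjustment for baseline area remains there.

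**Working it through.** **Inputs.** 200 subjects each on PM, PEOM and pooled sham; mean growth 1.47, 1.70 and 2.13 mm²/year, hence differences from sham of 0.66 and 0.43; SD 1.50 (SAP 3.4). Two-sided alpha is 0.0496 (SAP 6.2.1); the power table uses 0.0495.

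**Assumptions.** The documents give neither the correlation r of baseline area with Month 12 change nor the baseline distribution. I take overall linear r from 0 to 0.5 and three shapes on 2.5-17.5 mm²: uniform, truncated lognormal (median 7.5, log-SD 0.5) and truncated normal (mean 8, SD 4).

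**1. The plan's own power.** The standard error of a difference is 1.5 × √(2/200) = 0.15, so the noncentralities are 0.43/0.15 = 2.87 and 0.66/0.15 = 4.40. The noncentral t with 597 df at alpha 0.0495 gives 81.5% and 99.2%, matching SAP Table 1.

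**2. What the cut already captures.** Let c be the squared correlation of area with the indicator of 7.5 mm² or more. For the uniform shape the between-category variance is (1/3)(2/3)(12.5 - 5)² = 12.5, out of 15²/12 = 18.75, so c = 0.667. The lognormal and normal shapes give 0.651 and 0.640. The category therefore keeps 64-67% of a linear R².

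**3. Gross variance ratio**, category only over category plus continuous: (1 - c·r²)/(1 - r²). At r = 0.3 and c = 0.651 this is 0.9414/0.91 = 1.0345.

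**4. Charge for the extra parameter.** With k covariates the variance is inflated by 1 + k/(N - 3 - k - 1). At N = 600, k = 2 gives 1.00337 and k = 3 gives 1.00506, a ratio of 1.00169. The visit interaction adds one parameter per visit, so the Month 12 contrast pays for about one covariate. In the example, 1.0345/1.00169 = 1.033, an excess of 3.3%. A simulated Month 12 ANCOVA at N = 600 with an uninformative baseline gave a model-based variance ratio of 1.0018, in agreement.

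**5. Net results at N = 600** (ranges are over the three shapes; power at SD 1.50, alpha 0.0496):

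| r | Excess variance, category only | Equivalent subjects of 600 | PEOM power change (points) |
|---|---|---|---|
| 0 | -0.17% | -1 | -0.06 |
| 0.1 | 0.2% | 1 | +0.07 |
| 0.2 | 1.2-1.3% | 7-8 | +0.5 |
| 0.3 | 3.1-3.4% | 18-20 | +1.1 to +1.2 |
| 0.4 | 6.2-6.7% | 35-38 | +2.0 to +2.2 |
| 0.5 | 10.9-11.8% | 59-63 | +3.0 to +3.3 |

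Category-only PEOM power is 81.4% at r = 0 and 87.6-87.8% at r = 0.5. PM power changes by -0.01 to +0.14 points. Break-even r is about 0.07.

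**6. If growth levels off with size.** With growth flat above 9, 10 or 12 mm², the excess at r = 0.3 is 0.2-2.1% and the PEOM gain 0.1-0.8 points. At r = 0.5 these are about 1-7.5% and 0.3-2.1 points.

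**7. Size subgroups**, where the category drops out (r is still the overall correlation). For 7.5 mm² or more (N 290-400) the excess is -0.3%, 4.1-5.2% and 14.5-18.3% at r = 0, 0.3 and 0.5. Below 7.5 mm² (N 200-310) it is -0.3 to -0.5%, 0.6-1.3% and 3.2-5.4%.

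**8. Other subgroups.** At total N = 36, 60, 100, 150 and 300 the extra term costs 3.4%, 1.9%, 1.1%, 0.7% and 0.3% of variance if baseline does not predict growth. Break-even r is about 0.30, 0.23, 0.17, 0.14 and 0.10. In the smallest subgroups the term can make precision worse.

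**The case against.** The strongest reply is that the gain depends on a correlation the documents never give and is modest at moderate values. At r = 0.3 the standard error falls by only about 1.5-1.7%, and PEOM power under the current model is already about 83.7%. Adjusting for the randomisation stratum is a legitimate prespecified choice. SAP 6.2.1 calls the study positive on PM versus sham alone, which scarcely moves. All of this stands. It limits the size of the point but does not remove it, because the worst case is about one subject's worth of information.

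A reader might infer more than the documents support:

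- **That the analysis is biased or the power misstated.** Randomisation and prespecification make the two-level model valid. The stated power comes from a one-way ANOVA without covariates and reproduces.
- **That the SAP contradicts itself on GA area at other visits, its square root and percent change**, since SAP 6 calls for the baseline value of such endpoints. That list applies unless otherwise noted, and SAP 6.2.7.1, 6.2.7.2 and 6.4.2 expressly adopt the 6.2.2 model. The specific text governs.
- **That the protocol promised a continuous covariate and SAP 15, which opens "The following changes were made to the analyses specified in the protocol", conceals its removal.** The protocol ties the covariate to screening, as Protocol 7.1 does for the stratification factor, so the stratum reading is natural. No unrecorded departure is shown.
- **That r = 0.3 is worth some 9% of variance.** That holds only for a within-category r of 0.3. With c = 0.65 this needs an overall r² of 0.09/(0.35 + 0.09 × 0.65) = 0.22, or r of about 0.47. An overall r of 0.3 leaves a within-category r² of only 0.03-0.04.

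**Conclusion.** The point holds as an opportunity for precision, not a defect of validity. The primary model leaves out a continuous baseline value that is already collected, while the SAP's key secondary and most other modelled endpoints include theirs with a visit interaction. The likely range runs from a loss of 0.17% of variance to a gain of about 11-12%, or -0.06 to about +3.3 points of PEOM power, for overall linear r between 0 and 0.5. Gains are smaller if growth plateaus with size. The benefit falls on PEOM versus sham and on the size subgroups, chiefly the upper one. The result rests on the assumed r and baseline shapes, SD 1.50 and 200 subjects per group. The cost side depends on no assumption about r: it is 0.17% at N = 600 and still only 0.23% at N = 450.

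**What to change.** Before Month 12 unmasking:

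- Add continuous baseline GA area and its interaction with visit to the primary covariate list in SAP 6, to SAP 6.2.2 and to both model statements in Appendices 1.2.1 and 1.2.2. Keep the stratum term and its interaction.
- Carry both terms into the per-protocol, imputation-analysis and 24-month MMRMs of GA area. The analyses in SAP 6.2.7.1, 6.2.7.2 and 6.4.2 inherit the change because they use the 6.2.2 model; use the square root of baseline area for the square-root responses.
- In SAP 6.2.5 set one fixed rule: the continuous term enters only the two lesion-size subgroup models split at 7.5 mm², where the category drops out. All other subgroup models keep their present covariates.
- Leave the slope models in SAP 6.2.4.3 unchanged, since their response is GA area itself and includes the baseline visit.
- Record the change in SAP 15. Mirror it in APL2-303 if its primary model is the same; that plan was not available here.

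This is a free improvement in the sense that it needs no new data and costs about 0.2% of variance if baseline size does not predict growth. It does need one SAP version beyond 2.0 and coordination with APL2-303.
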